5.3.4. Time to Response

Definition

Time to first response is defined as the time from the date of first dose of daratumumab to the date of initial documentation of a response (PR or better). Those subjects without response will be censored either at PD, or in the absence of PD, at the last disease assessment before the start of subsequent therapy. Patients with no post baseline disease assessment will be censored on Day 1.

Time to best response is defined as the time between the date of first dose of daratumumab and the date of the initial evaluation of the best response (PR or better) to treatment. Subjects without response will be censored either at PD, or in the absence of PD, at the last disease assessment before the start of subsequent therapy. Patients with no post baseline disease assessment will be censored on Day 1.

Analysis Methods

The Kaplan-Meier method will be used to estimate the distribution of time to response and time to best response for each dose group for all treated subjects in Phase 1, and for ITT population in Phase 2.

In addition, descriptive statistics (mean, standard deviation, median, and range) will be provided to summarize time to first response and time to best response for responders in each treatment group.

5.3.5. Overall Survival

Definition

Overall Survival (OS) is defined as the number of days from administration of the first dose (Day 1) to date of death.

Data for patients who are alive at the date of last contact or have unknown status will be censored at the date of the last contact. Those patients who have withdrawn will be considered to be alive and censored at the date of withdrawal.

Analysis Methods

OS will only be analyzed for Phase 2.

OS will be estimated using the Kaplan-Meier method for the ITT population. No inferential analysis will be performed.

The Kaplan-Meier estimates will be plotted to produce a survival curve.

Kaplan-Meier estimates will also be plotted to produce the survival curves for responder vs. non-responder based on computerized algorithm.

5.4. Other Efficacy Variable(s)

5.4.1. Serum/Urine M-Protein or FLC Reduction

Definition

Serum/urine M-protein or FLC reduction, defined as the percent change from baseline at each post-baseline assessment visit in the quantitation of the corresponding serum/urine M-protein or FLC, according to the measurable type at baseline.

Analysis Methods

Waterfall plot will be generated for maximum percent reduction from baseline in serum/urine M-protein or FLC, based on the measurable type at baseline for all treated subjects in Phase 1, and for ITT population in Phase 2.

5.4.2. Change in Bone Marrow % Plasma Cells

Definition

Bone marrow % plasma cell is based on results from either biopsy or aspirate.

Analysis Methods

Among responders, a shift table of bone marrow % plasma cells ($< 5, \ge 5 - \le 10, > 10 - \le 30, > 30$) from baseline value to first post-baseline value will be provided. In addition, a figure will be generated to display the corresponding numeric change in bone marrow % plasma cells for responders.

6. SAFETY

For all treated subjects in Phase 1, and for safety population in Phase 2, the safety profiles of daratumumab or combination with Len/Dex will be evaluated by the incidence of adverse events (AEs), death, laboratory results, vital signs, physical examination findings, and ECG results.

Safety evaluations will be made by treatment actually received. The severity of AEs and the toxicity of laboratory parameters will be assessed using NCI CTC version 4.03. Adverse events are coded using MedDRA version 17.0.

6.1. Adverse Events

Unless otherwise specified, only treatment-emergent adverse events (TEAEs) will be summarized.

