9.1.4. Safety Follow-up Period

After their last dose of lenalidomide, subjects will be followed for 3 years to assess occurrence of new cancers. Investigators will be asked to contact the subjects every 3-6 months to collect this information. In case of the occurrence of a new cancer, the investigator must report this occurrence on an SAE form as described in Section 12.6.

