12.6. Procedures

As per Amendment 8, only SAEs and SPMs will be collected (see Table 4 and Attachment 9). The SAE and SPM data should be entered in the subject file/notes.

Any SPM that occurs during a subject's participation in the study or for 3 years after the last dose of lenalidomide is considered an immediately reportable event. It must be reported to the sponsor within 24 hours after the investigator has gained knowledge of it by using the SPM form attached to the regular SAE form.

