12.6.1. All Adverse Events

The investigator must report all directly observed AEs and all AEs reported by the subject, whether spontaneously or in response to general, nondirected questioning (eg, "How has your health been since the last visit?"). For each AE reported by the subject, the investigator should obtain all the information required to complete the AE page of the eCRF, in accordance with the guidelines that accompany it.

All adverse events and special reporting situations, whether serious or non-serious, will be reported from the time a signed and dated ICF is obtained until 30 days after the last dose of any component of the treatment regimen. As of Amendment 7, only SAEs will be collected (see Table 3 and Attachment 8). Nonserious medical events (signs, symptoms, diagnosis) that occur between the Screening Visit or before the first infusion and the first study drug treatment at Cycle 1 Visit 1 should be documented in the medical history. All AEs that occur in subjects during the AE reporting period must be reported, whether or not the event is treatment related.

Serious adverse events, including those spontaneously reported to the investigator within 30 days of the last dose of any component of the treatment regimen, must be reported using the Serious Adverse Event Form. The sponsor will evaluate any safety information that is spontaneously reported by an investigator beyond the time frame specified in the protocol.

All adverse events, regardless of seriousness, severity, or presumed relationship to study drug, must be recorded using medical terminology in the source document and the CRF. Whenever possible, diagnoses should be given when signs and symptoms are due to a common etiology (eg, cough, runny nose, sneezing, sore throat, and head congestion should be reported as "upper respiratory infection"). Investigators must record in the CRF their opinion concerning the relationship of the adverse event to study therapy. All measures required for adverse event management must be recorded in the source document and reported according to sponsor instructions.

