2.6.12. Treatment Emergent Adverse Events

Treatment emergent adverse events (TEAEs) are defined as any AE with onset date and time on or after that of the first dose of study drug infusion through 30 days after the last dose of study drug or the day prior to start of subsequent therapy, whichever is earlier; or any AE that is considered related to (probably, or possibly related) study drug regardless of the start date of the event. AEs with missing or partial onset date and time will be considered as treatment-emergent unless the onset date and time of an AE can be determined as earlier than that of the first dose, or later than 30 days after last infusion .

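### New cancers are collected for 3 years after lenalidomide, but the SAP plans no second primary malignancy summary, and late cases reach the AE tables only if judged related

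*SAP*

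**What the plan says.** **Collection.** Protocol 9.1.4: "After their last dose of lenalidomide, subjects will be followed for 3 years to assess occurrence of new cancers". When one occurs, "the investigator must report this occurrence on an SAE form as described in Section 12.6". Protocol 12.6 makes the event immediately reportable over the same period: "Any SPM that occurs during a subject's participation in the study or for 3 years after the last dose of lenalidomide". This is a deliberate extension, because Protocol 12.6.1 collects other adverse events only "until 30 days after the last dose of any component of the treatment regimen".

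**Analysis.** SAP 6.1 states that, unless otherwise specified, "only treatment-emergent adverse events (TEAEs) will be summarized". SAP 2.6.12 defines treatment-emergent in two limbs. The time limb runs from first dose "through 30 days after the last dose of study drug or the day prior to start of subsequent therapy, whichever is earlier". The relatedness limb adds "any AE that is considered related to (probably, or possibly related) study drug regardless of the start date of the event". The adverse events of clinical interest in SAP 6.1.2 are infusion-related reactions, infections/infestations and neutropenia. No section of the SAP defines a table or listing of SPMs. Protocol 11.11 has the same restriction, to onset during the treatment phase.

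**Other places where an SPM could appear.** SAP 6.2 summarises all deaths during the study with primary cause. Under Protocol 11.13 the IDMC reviews new cancers at least every 6 months, but not after the primary analysis.

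**Scope.** SAP 1 states that the plan is for the primary analysis. Protocol 3.1 places that about 12 months after the last subject's first dose, with an updated safety analysis at about 24 months reported in a CSR addendum.

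**The concern.** The primary objective is the safety profile of the combination. The protocol runs an off-treatment follow-up for one late event type, but the analysis rule stops shortly after treatment does. An SPM arising in between is collected and reported to the sponsor, yet the SAP gives it no place in the safety tables unless it is attributed to study drug or is fatal.

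Two things are at stake. The SPM count would be incomplete, and whether a late case is counted would rest on a causality judgement made in an open-label, uncontrolled study. With 42 to 58 subjects planned, few SPMs can be expected, so leaving out even one could change how the result reads. SAP 3 also says that the data cut is meant to support a BLA submission.

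**Working it through.** The plan gives no SPM figure to reproduce, so the check is a reading of the rules followed by an illustration.

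**Step 1: where each kind of SPM lands.**

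| SPM | Planned place |
|---|---|
| Onset within 30 days of last dose and before subsequent therapy | TEAE tables by SOC and PT |
| Later onset, judged possible or probable | TEAE tables, by the relatedness limb |
| Later onset, fatal | Deaths summary, by cause |
| Later onset, non-fatal, judged not related or doubtful | None |
| Later onset, non-fatal, rated very likely | None, on a literal reading (Step 2) |

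**Step 2: the relatedness categories differ.** SAP 2.6.11 and 2.6.12 count possible and probable as related. Protocol 12.4.1 counts possible, probable and very likely, and 12.4.2 defines all three. Read literally, a late SPM in the strongest category misses the relatedness limb. This is presumably unintended.

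**Step 3: illustration at the SAP's own cutoff.**

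Inputs from the documents:
- The TEAE tail is 30 days, which is 30 ÷ (365.25/12) = 0.99 month (month as defined in SAP 2.6.5).
- Observation is L = 12 months per subject, the minimum planned for the last-enrolled subject.

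Assumptions, none of them in the documents:
- A fraction d of subjects stops all study drug at month t, and the rest stay on treatment.
- The SPM rate is constant and follow-up is complete to the cutoff.
- No subsequent therapy starts within the 30 days.
- No late SPM is judged related.

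Share of SPMs outside the window = d × (L − t − 0.99) / L. With t = 3 this is d × 8.01/12 = d × 0.668:
- d = 25%: 17%
- d = 50%: 33%
- d = 75%: 50%

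If those subjects stop at month 6 instead, the factor is 5.01/12 = 0.418, giving 10% at d = 25% and 21% at d = 50%. With L = 18 and t = 3, the factor is 14.01/18 = 0.779, giving 19% and 39%. Any share q of late SPMs judged related multiplies each result by (1 − q).

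**Step 4: how the picture changes with full follow-up.** After T months of treatment and a complete 36 months of follow-up, with the same constant rate and none judged related, the share outside is (36 − 0.99)/(T + 36):
- T = 12: 73%
- T = 24: 58%
- T = 36: 49%

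The share is above one half only for T below about 34 months. If 25% of late SPMs are judged related, the three figures become 55%, 44% and 36%. These describe the end of follow-up, well after the analysis this SAP governs.

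**The case against.** The strongest reply is that the SAP does what the protocol asks. Protocol 11.11 limits the analysis to treatment-phase onset, and SPM is named in no objective or endpoint. At the primary analysis most of the 3-year follow-up has yet to happen. SPMs in the window and late ones judged related are tabulated, fatal ones appear under deaths, the IDMC sees new cancers up to the primary analysis, and each SPM must be reported within 24 hours.

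Much of this stands, and it limits the size of the problem. It does not close the gap:
- The shared restriction in Protocol 11.11 means that neither document plans to analyse the SPM data.
- Expedited reporting and IDMC review are not tables in the study report.
- The deaths summary misses non-fatal cases.
- Subjects who stopped early already have off-treatment time at the primary cutoff.
- The 24-month update has no SPM method in these documents.

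A reader might go further and infer that most SPMs would go uncounted. For example, 6 months of treatment followed by a full 36 months of follow-up puts only about 7 of 42 months (17%) inside the window. The documents do not support that inference for this SAP. At 12 months of observation the same subject has about 7 of 12 months (58%) inside the window. The 6-month duration has no source, since treatment runs to progression or unacceptable toxicity. A reader might also suppose that Phase 1 contributes long off-treatment follow-up, but no stop dates are given, and the Amendment 6 rationale describes Phase 1 subjects as on treatment for more than 12 months.

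**Conclusion.** The gap is real and worth correcting. The protocol collects SPMs for 3 years after lenalidomide. The SAP defines no SPM summary or listing, and its default rule leaves out late, non-fatal SPMs not judged related. SPM incidence would be undercounted and would depend on attribution.

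The size cannot be derived from the documents, which give no SPM rate, no stopping pattern and no share judged related. The 17% to 33% in the illustration rests on the assumptions in Step 3 and shows only that the loss need not be trivial at the primary analysis. The conclusion itself does not depend on that range; it follows from the definitions alone.

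**What to change.** 1. Add SPM to SAP 6.1.2 as a stated exception to the TEAE rule. Give the number and percentage of subjects with any SPM from first dose to the data cutoff, regardless of the TEAE window, subsequent therapy or attribution.
2. Add a listing with SPM type, onset relative to first and last dose, any subsequent therapy before onset, attribution and outcome.
3. If follow-up time is shown as context, define its end date for SPM ascertainment. The general follow-up in SAP 2.6.9 uses the latest date of any evaluation and is a different quantity. With so few subjects, a rate per person-time is optional.
4. Carry the same table and listing into the 24-month safety update.
5. Align the related categories in SAP 2.6.11 and 2.6.12 with Protocol 12.4.1.

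The cost is one table, one listing and a wording change. Some reconciliation may also be needed, because Protocol 12.6 has SPMs reported on a form attached to the SAE form and, from Amendment 8, entered in the subject's file or notes.

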6.1.1. Treatment Emergent Adverse Events

The following summaries will be provided for all TEAEs:

- An overview of TEAE will be provided, including the incidence of TEAE, serious TEAE, maximal severity of TEAE, treatment discontinuation due to TEAE, TEAE leading to treatment interruption, and death due to TEAE.
- An overview of TEAE by subgroups specified in Section 2.4
- Separate listings for each category above.

In addition, the following summaries will be generated:

- TEAEs by system organ class (SOC) and preferred term (PT)
- Most common (at least 5%) TEAEs by system organ class (SOC) and preferred term (PT)
- TEAEs by SOC, PT, and grade 3 or 4.
- TEAEs by SOC, PT, and worst toxicity grade
- TEAEs by SOC, PT, and relationship to study medication
- Most common (at least 10%) TEAEs by system organ class (SOC), preferred term (PT), and grade 3 or 4.
- TEAEs by SOC, PT, and grade 3/4 by subgroups specified in Section 2.4
- Serious TEAEs by SOC and PT
- Serious TEAEs by SOC, PT, and worst toxicity grade
- Serious TEAEs by SOC, PT, and relationship to study medication
- Most common (at least 1%) serious TEAEs by system organ class (SOC) and preferred term (PT)
- Grade 3 or 4 TEAEs by SOC and PT
- Grade 3 or 4 TEAEs by SOC, PT, and relationship to study drug

The following summaries for TEAEs leading to treatment modifications will be provided:

- TEAEs leading to infusion interrupted by PT, and relationship to study drug
- TEAEs leading to infusion prolonged by PT, and relationship to study drug.
- TEAE leading to hospitalization or prolonged hospitalization by SOC and PT.
- Treatment discontinuation due to TEAEs by PT and relationship to study drug
- Study discontinuation due to TEAEs by PT and relationship to study drug
- Death due to TEAEs by PT and relationship to study drug.

6.1.2. Adverse Events of Clinical Interest

6.1.2.1. Infusion Related Reactions

For each phase, the infusion related reactions (IRRs) will be clinically reviewed and identified. The incidence of IRRs will be presented by SOC, PT, and toxicity grade (any grade and grade 3 or 4). The incidence of IRRs will also be presented by type of pre-infusion steroids.

The time to onset of infusion related reaction will be summarized.

All infusion related reactions will be also listed.

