9.2.1.4. Electrocardiogram	Text deleted: Digital ECGs will be transmitted from the sites electronically to a central laboratory (eResearch Technology, Inc) for a treatment-blinded measurement of the cardiac rhythm and assessment of morphology by a central cardiologist.			
Rationale: Alignment with other daratumumab protocols.				
12.6.1. All Adverse Events	Text revised to state that adverse events will be collected within 30 days of the last dose of any component of the treatment regimen.			
Rationale: Subjects may continue daratumumab treatment beyond 24 cycles.				
Table 2 (Phase 2 Time and Event Schedule)	Changed range of Study visits column header from "7-24" to "7+".			
Rationale: Minor errors were noted				
Throughout the protocol	Minor grammatical, formatting, or spelling changes were made.			

Amendment 5 (26 February 2014)

This amendment is considered to be substantial based on the criteria set forth in Article 10(a) of Directive 2001/20/EC of the European Parliament and the Council of the European Union.

The overall reason for the amendment: This amendment included defining the change in sponsor to Janssen Research & Development (JRD) and converting to the JRD protocol template. Additionally 10 of the approximately 30 subjects enrolled on Phase 2 will have shortened infusion times for the first daratumumab infusion to evaluate the safety and incidence of infusion related reactions when infusion time is shortened. Eligibility criteria have also been modified to remove the cap placed on prior lines of therapy to allow a broader population to be studied in Phase 2.

Applicable Section(s) Description of Change(s)											
Rationale: JRD has taken over resp daratumumab.	onsibility of this study from Genmab A/S in a partnership effort to develop										
Global	Changed sponsor name from Genmab A/S to Janssen Research & Development										
	edules were revised to reflect the changes made in the assessments for the study y by adding separate tables for assessment in Phase 1 and Phase 2.										
Table 1 and Table 2 Time and Event Schedules	Revised Table 1 (Time and Event Schedule) to reflect changes in the protocol. Added Table 2 (Time and Event Schedule for Phase 2 which includes pharmacokinetic/immunogenicity and exploratory biomarker assessments) for clarity										
Rationale: A secondary objective w	ras added to evaluate immunogenicity using JRD analysis methods.										

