6.1. Daratumumab

Daratumumab will be administered as an IV infusion. Each subject's dose will be calculated based on the subject's weight rounded to the nearest kilogram, ie, assigned cohort dose in $mg/kg \times body$ weight in kg. The dose does not need to be recalculated for weight changes that are <10% from baseline. The weight will be used to determine the number of vials required for dosing. The pharmacist will then calculate the required volume of daratumumab from the number of vials needed for each subject. For subjects whose body mass index is greater than 30 kg/m^2 , the investigator should use a weight that, based on the subject's height, corresponds to a maximum body mass index of 30.

For Phase 1, daratumumab will be given as follows:

- Cycle 1: Day 0 (predose infusion), Day 1 (first full-dose infusion), and Days 8, 15, and 22 of a 28-day cycle
- Cycle 2: Days 1, 8, 15, and 22 of a 28-day cycle
- Cycles 3-6: Days 1 and 15 of a 28-day cycle for 4 cycles or until the subject experiences unacceptable toxicity or disease progression, whichever comes first
- Cycles 7+: Day 1 of a 28-day cycle until the subject experiences unacceptable toxicity or disease progression, whichever comes first

For Phase 2, daratumumab will be given as follows:

- Cycle 1: Day 1 (first full-dose infusion), and Days 8, 15, and 22 of a 28-day cycle
- Cycle 2: Days 1, 8, 15, and 22 of a 28-day cycle
- Cycles 3-6: Days 1 and 15 of a 28-day cycle for 4 cycles or until the subject experiences unacceptable toxicity or disease progression, whichever comes first
- Cycles 7+: Day 1 of a 28-day cycle until the subject experiences unacceptable toxicity or disease progression, whichever comes first Table 5 and Table 6 provide recommendations for the rate of infusion.

Table 5: Phase 1 Infusion Rate Recommendations

Predose	Infusions	First Full-do	ose Infusion ^a	Subsequent Full-dose Infusions ^a			
Time (minutes)	Rate (mL/hour)	Time	Rate (mL/hour)	Time (minutes)	Rate (mL/hour)		
		(minutes)					
0 - 240	12.5	0 - 60	50	0 - 60	50°		
		61 – 180	100	61 - 120	100		
		181 -	150 ^b	121 - 180	150		
				181 -	200		
Total volume	50 mL	Total volume	1000 mL	Total volume	1000 mL		

^a Additional details for administration times and rates for the full-dose infusions will be provided in the administration guidelines.

Table 6: Phase 2 Infusion Rate Recommendations

	e Infusion for y 20 Subjects ^a		e Infusion for y 10 Subjects ^a	Subsequent Full-dose Infusion for all subjects ^a			

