4.4. Extent of Exposure

Descriptive statistics will be provided by dose group and overall for total number of pre-dose (Phase 1 only) and full daratumumab infusions, treatment duration (the interval between date of first infusion and date of last infusion), total dose (mg) received from pre-dose and full infusions, and relative dose intensity (calculated for each full-infusion as the ratio of dose intensity (mg/kg) and the planned dose level (mg/kg)).

The number and percent of patients with incomplete daratumumab infusions (i.e. total volume of infusion not administered) and reason for incomplete infusion will be summarized by dose group, visit and overall.

The duration of daratumumab infusions (hours) will also be summarized.

All infusions will be listed by patient and visit. For Phase 1, both pre-dose and full infusions will be listed.

Exposure to lenalidomide and dexamethasone (dose and duration) will be also summarized separately by dose group, visit and overall.

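### The SAP plans no summary of infusion-related reactions or infusion duration by first-infusion schedule, so its tables do not address the documented reason for the shortened first infusion

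*SAP*

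**What the plan says.** The overall reason given for Amendment 5 in the Protocol Amendments section states: "Additionally 10 of the approximately 30 subjects enrolled on Phase 2 will have shortened infusion times for the first daratumumab infusion". The purpose given is "to evaluate the safety and incidence of infusion related reactions when infusion time is shortened". The current text keeps both schedules. In Protocol Section 6.1, "Table 6: Phase 2 Infusion Rate Recommendations" has one first-infusion column for about 20 subjects (1000 mL), another for about 10 (500 mL), and a single column for all later infusions in everyone (500 mL).

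SAP 6.1.2.1 sets the level of analysis: "For each phase, the infusion related reactions (IRRs) will be clinically reviewed and identified". Incidence is tabulated by system organ class, preferred term and grade (any; 3 or 4), and time to onset is summarised. The one further breakdown is: "The incidence of IRRs will also be presented by type of pre-infusion steroids". A listing is also planned: "All infusion related reactions will be also listed".

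SAP 4.4 summarises infusion duration in hours without naming a grouping and adds: "All infusions will be listed by patient and visit". SAP 6.1.1 tabulates events leading to interrupted or prolonged infusions by preferred term and relationship. None of these sections refers to first-infusion schedule or separates the first infusion from later ones.

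**The concern.** Safety is the primary objective, adverse event incidence is the primary endpoint, and the SAP treats IRRs as events of clinical interest. Protocol Section 6.6 asks for particular care at the first full-dose infusion, which is the one that differs between the two groups. The protocol records why about a third of Phase 2 received it faster, and the analysis plan then has no table that looks at that third. SAP Section 3 says the data cut is meant to support a BLA submission, so the planned tables are what a regulator would read first. A single Phase 2 IRR rate, onset time or infusion duration would describe a mixture of two regimens, and a difference between them would not be visible.

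**Working it through.** **1. Does any other rule in the plan supply the split?**
- SAP 2.4 marks only age and sex for safety subgroups.
- SAP 4.4 groups exposure by dose group and, for some items, by visit. Phase 2 has one dose level, so dose group does not separate the schedules.
- Protocol 11.1 presents results by cohort, but Protocol 5.1 makes Phase 2 a single expansion cohort.

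Nothing supplies it.

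**2. How different are the two first infusions?** These are Table 6 rates, uninterrupted.
- 1000 mL schedule: 1 h at 50 mL/h plus 2 h at 100 mL/h delivers 50 + 200 = 250 mL in 3 h. The remaining 750 mL at 150 mL/h takes 5 h. Total 8 h = 480 min.
- 1000 mL with the permitted step to 200 mL/h after 2 h at 150 mL/h: 250 + 300 = 550 mL in 5 h, then 450/200 = 2.25 h. Total 7.25 h = 435 min.
- 500 mL schedule: 50 + 100 + 150 = 300 mL in 3 h, then 200/200 = 1 h. Total 4 h = 240 min. The footnote allowing a higher starting rate depends on a previous full-dose infusion, so it is not applied to a first infusion.

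A pooled mean first-infusion duration would be (20 × 480 + 10 × 240)/30 = 400 min, or (20 × 435 + 10 × 240)/30 = 370 min. Neither group is planned to have either value.

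**3. What can a pooled IRR rate conceal?** The documents give no IRR rates, so these counts are assumptions. Intervals are exact (Clopper-Pearson) 95%.

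| 1000 mL (n = 20) | 500 mL (n = 10) | Pooled |
|---|---|---|
| 8/20 = 40% (19.1 to 63.9) | 6/10 = 60% (26.2 to 87.8) | 14/30 = 47% |
| 10/20 = 50% (27.2 to 72.8) | 4/10 = 40% (12.2 to 73.8) | 14/30 = 47% |
| 6/20 = 30% (11.9 to 54.3) | 7/10 = 70% (34.8 to 93.3) | 13/30 = 43% |

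The first two rows point in opposite directions and give the same pooled figure. Any-infusion incidence blurs the picture further, because later infusions follow one schedule for everyone.

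**4. What could a split deliver?**
- With no events, the exact upper limit is 1 − 0.025^(1/n): 30.8% for 0/10, 16.8% for 0/20 and 11.6% for 0/30.
- If the true rate of a severe reaction were 5%, none would be seen in ten subjects with probability 0.95^10 = 0.60. At 10% the probability is 0.90^10 = 0.35.
- The half-width of a 95% interval for the difference, 1.96 × √[p(1 − p)(1/10 + 1/20)], is 34.8 points at p = 0.3 and 38.0 at p = 0.5.
- Fisher exact power (two-sided 0.05, 20 against 10) is 15% for 30% against 50%, 11% for 40% against 60%, and 45% for 30% against 70%.
- Detecting a 20-point difference with 80% power needs about 93 to 97 per group.

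The only sample-size figures in the plan (Protocol 11.2, SAP 1.4) concern overall response. They reproduce: with success at 20 or more of 30, exact power is 89.4% at 75% and 97.4% at 80%, against the stated 89% and 97%. No figure is given for IRRs.

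**The case against.** The omission can be read as minor, and much of that case stands. The purpose appears only in the Amendment 5 rationale, not among the objectives or endpoints, and no formal test is planned. Amendment 5 also cites earlier single-agent infusion data as a reason to adjust Phase 2 rates, so the change was partly operational. An overall Phase 2 IRR rate does address the primary objective as written. Table 6 gives recommendations, which the sponsor or IDMC may modify and the investigator may adjust, so the two columns are not treatment arms. The SAP refers to table shells that are not in these documents, so pooling of duration is inferred from the text naming no grouping.

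A reader might infer three stronger things, none of which the documents support.
- That the trial cannot say anything about the shorter infusion. All IRRs and all infusions are listed, Protocol Section 7 records start and stop times and the amount infused, and SAP 2.6.8 derives duration per infusion. A descriptive split could be built afterwards.
- That the two schedules were meant to be compared. The amendment speaks of evaluating reactions under the shorter infusion.
- That a split would show the shorter infusion to be as well tolerated. The documents do not say how the ten subjects are chosen, volume and rate change together, and Step 4 shows how little ten subjects can exclude.

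The objection does not remove the gap. A listing leaves the reader to build the table without a prespecified rule for who belongs to which schedule.

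**Conclusion.** The concern holds as a reporting omission in the SAP. Its planned tables contain no IRR or infusion-duration summary by first-infusion schedule, although the protocol records evaluation of IRRs as the reason for the shorter schedule and the current text still uses both. The two first infusions differ about twofold in planned duration (435 to 480 against 240 minutes). Data collection and the listings are unaffected. The split has modest value: it makes each regimen's experience visible and supports no inference about their difference. The durations assume uninterrupted infusion at Table 6 rates; the IRR counts are illustrations only; group sizes are the approximate 20 and 10 of Table 6.

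**What to change.** In SAP 6.1.2.1 and 4.4, for Phase 2:
- Tabulate first-infusion IRRs (any grade; grade 3 or 4), time to onset, interruptions and infusion duration by planned first-infusion schedule (1000 mL, 500 mL), with n/N and exact 95% intervals for proportions.
- Report IRRs at later infusions separately.
- State that membership follows the assigned schedule whatever the later rate changes, and name the data source for the assignment. The documents do not identify a field for it.
- Label the table descriptive. Note that no randomised allocation to schedule is described, that volume and rate change together, and that about ten subjects received the shorter infusion.

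No new clinical data are needed, provided the assignment is on file. The cost is a few extra table rows with wide intervals, and some risk that readers over-interpret a chance difference, which the label is there to limit.
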